# Phase II Hypotheses:

**AIM 1 Hypotheses:** Children of fathers who receive F4C (n=180), relative to BIP (n=180), will: (1a) experience less family violence (FV), (1b) have more positive father-child interactions, and (1c) have lower FV-related mental health symptoms (PTSD, internalizing/externalizing) at post treatment and 6- and 12-month follow-ups. The effects of both treatments on father and coparent mental health outcomes will also be examined (1d exploratory). Hypotheses will be evaluated with the broad family of latent (growth) curve models (LGM), which estimate and compare trajectories of change for each case in the data. Group differences in changes will be tested in multiple group LGM models. Following analyses for our primary study hypotheses, we will examine whether child sex moderates child mental health outcomes between the F4C and BIP groups. Power. The planned sample size of 140 F4C and 140 BIP cases provides power of .91 to detect a small to moderate effect size (d = 0.12). The current study with 140 per group (even 126) per group assuming a conservative 30% attrition at follow-up) has sufficient power to determine small differences in changes between intervention groups on outcomes. LGM models for changes in latent rather than observed scores, for three or more waves of data, have the advantage of partialing out measurement error, and increasing the statistical power by at least 20%. See Statistical Design and Power Section for estimation method.

AIM 2 Hypotheses. Compared to BIP, more F4C fathers will show profiles of healthy change in therapeutic targets: (2a) masked coding of in-session RF/ ER (i.e., increased RF and adaptive ER, decreased maladaptive ER), and (2b) between-session self-reported RF/ ER (i.e., increased

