RF and adaptive ER, decreased maladaptive ER). F4C change profiles will reveal critical junctures in treatment that precipitate therapeutic change, thereby serving to optimize timing and delivery of treatment components (2c, exploratory). Group-based trajectory modeling from the family of latent growth mixture modeling (GMM) will be used first to examine the number of different trajectory groups and their profiles (e.g., stable low or high adaptative ER, gradual increase or decrease in RF level, initial increase, then stable RF level, rapid decrease followed by gradual decrease of maladaptive ER, etc.) during the intervention period, as well as determine whether F4C vs. BIP treatment conditions influence trajectory group membership. Initially, trajectories of each in-session and between-session therapeutic change target will be modeled separately. Because data are expected to have unequal measurement intervals, we will use a new feature in Mplus 8.8 for analyzing such data (i.e., *tinterval and dynamical SEM*), and explore a new Stata 17 module for irregular time spacing measurements (i.e., xtusreg).143 Subsequent models will simultaneously examine various combinations of these six related targets to identify appropriate group membership for the fathers. This therapeutic change grouping will be modeled as the mediating variable in subsequent mediation analyses. **Power.** Determining power in group-based trajectory modeling with unequal time gaps is complex and not well explored. Given that some applications have used the classical, similar analytic method, mixture LGM (with equal time gaps), to extract three classes with a sample size as low as 45,144 the current target sample size of 360 (or 252 with attrition) will be adequate to identify trajectory groups and test further differences between F4C and BIP groups.

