**AIM 3. Hypotheses.** Profiles of healthy change in RF and ER will mediate the treatment effect of F4C over BIP on: (3a) FV (3b) father-child interactions, and (3c) child mental health (PTSD, internalizing/externalizing) at post-treatment and at 6- and 12-month follow-ups. LGM mediation models will be used to evaluate the mediating effect of therapeutic change classes on the treatment impact on both the fathers' use of FV and children's outcomes. In particular, the baseline predictor will be father's randomly assigned intervention group: F4C vs. BIP, with father's therapeutic change in RF and ER trajectory groups from Aim 2 entered as a categorical mediator into a structural equation model framework to investigate the mechanisms of change in child outcomes at post-intervention and up to two subsequent follow-ups. **Power.** Power analyses for mediational LGM models with categorical mediators are rare. The specialized Mplus 8.8 SEM software however has been advancing the toolbox available for such complex models, and its recent capabilities promise to provide adequate statistical power with the proposed sample size.

4. **Participant Population:** Provide a detailed description of the types of participants who will be recruited into this study.

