# Phase II:

The target sample is 280 father-coparent dyads and their 9 months to 11 year-old children recruited from CPS-involved families referred to the Parent and Family Development Program (PFDP) at Yale or the UCONN Health Center Outpatient Psychiatry Clinic. Participants will be randomized to either F4C (n = 140) or BIP (n = 140) following a baseline assessment. Half of F4C and BIP families will be treated at Yale and half at UConn Health. Yale will serve families in

Greater New Haven region, while UConn Health will serve families in the Greater Hartford region. The two sites are approximately a 45-minute drive apart.

5. **Describe** how access to the population will be gained in the study.

Fathers referred to the Parent and Family Development Program or UCONN Health Center by the CT Department of Children and Families (DCF) or the community due to IPV or child maltreatment risk will be provided information about the study and asked to complete an initial brief screening if they are interested in participation. He will be told that his screening questionnaire (which will include demographic matching information such as age, ethnicity, city of residence, income, employment history, SA history etc.) will be reviewed and he will be contacted to set up further assessment sessions if he is found eligible by the PI based on our study's requirements. This will provide the opportunity for contact with the mother to conduct phone screening with her related to IPV and her willingness for their shared child to participate. Female co-parent and intimate partner contact information will be provided on the referral from DCF or community referral source so that fathers are not providing this information, and this will limit the possibility of coercion.

6. **Participant classification:** Check off all classifications of participants that will be specifically recruited for enrollment in the research project. Will participants who may require additional safeguards or other considerations be enrolled in the study? If so, identify the population of participants requiring special safeguards and provide a justification for their involvement.

🛛 Healthy	□Fetal material, placenta, or dead fetus
Prisoners	□Economically disadvantaged persons
🗆 Employees	□Pregnant women and/or fetuses
□ Females of childbearing pote	ential
	
 
Healthy
 
Prisoners
 
Employees
 
Females of childbearing pote
 

Click or tap here to enter text.

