# 4. How was this estimate derived?

Phase I: Seventy-five fathers, the female co-parent of their youngest child, and their child will participate for a total of up to 225 participants. We intend to include all 75 fathers assigned to study interventions for intent to treat analysis. The planned sample size of 75 participants who will provide data for inclusion in our intention-to-treat analysis should provide sufficient power to detect clinically meaningful differences between and within treatment conditions as specified in our primary aims. A sample of 63 people provides power of 80% to detect a standardized treatment group differences at 18 weeks of d = 0.45. For purposes of power estimates, we assumed d = 0.45 will represent a potentially meaningful clinical difference in both our primary and mechanism outcomes. In a pilot study examining F4C on participant IPV effect size for outcome was d = 0.86. We will enroll 75 participants to accommodate a 16% loss to follow-up.

Using these procedures in prior studies, our rate of successful follow-up has ranged from 70-90%. With 280 participant families randomized and an aim of at least 70% completion, we expect to have 196 cases with complete treatment and follow-up data.

**4. Process of Consent/Assent** (*NOTE: When a study includes minors, parent provide permission [not consent] for the child's participation, and the child provides assent for participation)* 

Describe the setting and conditions under which consent/assent will be obtained, including parental permission or surrogate permission and the steps taken to ensure participants' independent decision-making.

Fathers will complete informed consent either in person or online via Yale's REDcap data system, in line with guidance on obtaining informed consent during the COVID-19 pandemic. Each will agree to have their female co-parent contacted for consent of participation of their shared child.

Mothers will complete informed consent related to their own participation and the participation of children in which they are the primary guardian. This will be completed online via Yale's REDcap system..

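### The Aim 2 and Aim 3 adequacy claims rest on a class-extraction precedent, on software and on a sample of 360 that the design does not have; no detectable class-share difference is given

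*Combined protocol and SAP*

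**What the plan says.** Hypotheses 2a and 2b (Section IV, Aims for Phase II and Phase II Hypotheses) predict that more F4C than BIP fathers show healthy-change profiles in reflective functioning and emotion regulation. The analysis fits trajectory groups over the intervention period and asks whether treatment arm influences membership.

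The AIM 2 power paragraph begins with a caution: "Determining power in group-based trajectory modeling with unequal time gaps is complex and not well explored". It then cites applications with equal time gaps that extracted three classes from as few as 45 cases, gives a target of 360 (252 with attrition), and concludes that this "will be adequate to identify trajectory groups and test further differences between F4C and BIP groups". It states no alpha, class share, effect size or power value.

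The AIM 3 paragraph says power analyses for such models are rare, and of the software says that "its recent capabilities promise to provide adequate statistical power with the proposed sample size".

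The sample size elsewhere is different. Participant Population, Phase II: "Participants will be randomized to either F4C (n = 140) or BIP (n = 140) following a baseline assessment". Section V, under the derivation of the enrolment estimate: "we expect to have 196 cases with complete treatment and follow-up data".

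The plan gives three effect sizes, none of them for class membership: d = 0.12 (Phase II, Aim 1), d = 0.86 (pilot, intimate partner violence) and, in the Phase I sample-size paragraph, "we assumed d = 0.45 will represent a potentially meaningful clinical difference in both our primary and mechanism outcomes".

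**The concern.** Finding classes in one sample and comparing class shares between two randomised arms are different tasks. The first depends on how well the trajectories separate. The second depends on the number per arm, the class shares and the size of the shift between arms. A precedent for the first cannot support a claim about the second, whichever total is written into the sentence. The precedent also used equal time gaps, and this trial expects unequal ones.

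The total is wrong as well, since 360/252 does not belong to a 280-father design. Aim 3 inherits the problem because the Aim 2 classes are its mediator.

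At stake is how a null mechanism result can be read. Without a stated detectable difference, a reader cannot tell an uninformative null from an informative one.

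**Working it through.** **Sample size.** 360 × 0.70 = 252, so the Aim 2 pair is internally consistent. For the actual design, 280 × 0.70 = 196, or 98 per arm. The same slip appears in Aim 1, where 126 per group is 180 × 0.70; 140 × 0.70 = 98.

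**Plan figure.** Aims 2 and 3 state no power value, so there is none to reproduce.

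**Assumptions (mine; the plan gives none).** Two-sided 5%; one target; classes known without error; BIP healthy-class share p_B of 20–50%. F4C share p_F = Φ(Φ⁻¹(p_B) + d).

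**Formula.** With n per arm, p̄ = (p_B + p_F)/2, SE₀ = √(2p̄(1−p̄)/n) and SE₁ = √((p_B(1−p_B) + p_F(1−p_F))/n):

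power = Φ((p_F − p_B − 1.96·SE₀)/SE₁), plus a small opposite tail.

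**Worked case, p_B = 0.50, d = 0.45.** p_F = 0.674, difference 0.174.
- n = 98: SE₀ = 0.0703, SE₁ = 0.0692; (0.1736 − 0.1379)/0.0692 = 0.52; power 0.70.
- n = 140: SE₀ = 0.0589, SE₁ = 0.0579; (0.1736 − 0.1154)/0.0579 = 1.01; power 0.84.

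**Power over p_B = 20–50%.**

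| d | source in plan | 98 per arm | 140 per arm |
|---|---|---|---|
| 0.12 | Aim 1, Phase II | 9–10% | 11–13% |
| 0.45 | Phase I planning, including mechanism outcomes | 64–71% | 79–85% |
| 0.86 | pilot IPV | >99% | >99% |

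At the sizes the paragraph implies, d = 0.45 gives about 89–93% (180 per arm) and 75–81% (126). The wrong total therefore flatters power by roughly 7–11 points at that effect.

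**Sensitivity at d = 0.45.**
- Class-assignment error of 15% each way, p_B = 0.50: shares 0.50 v 0.85 × 0.674 + 0.15 × 0.326 = 0.622; power 40% (98) and 54% (140).
- Bonferroni over the six targets (0.05/6), p_B = 0.50: 43% and 62%.
- Converting d by the logistic rule OR = exp(dπ/√3) instead: about 71–81% (98) and 86–93% (140).

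**Detectable difference, 80% power.** 14.9–16.7 points at 140 per arm; 18.1–19.9 at 98. For the cited precedent, 45 cases in two arms is about 22 each, which needs a gap of about 38–41 points.

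**Aim 3.** A joint-significance test requires both the arm-to-class and the class-to-outcome path to be significant. Pr(both) ≤ Pr(first), so its power is capped by the Aim 2 arm comparison on the same cases.

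**The case against.** The plan is candid that power for these models is poorly understood, and it offers no figure that could be called miscalculated. That is fair, but it does not rescue a conclusion of adequacy.

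A reader might go further and infer that, at the planned size, the class comparison fails on the plan's own effect sizes generally. The documents do not support that. At 140 per arm, d = 0.45 gives about 79–85% with error-free classes, and d = 0.86 gives over 99%, although the latter is a violence outcome rather than a mechanism. A clear shortfall at the planned size exists only at d = 0.12. That value belongs to Aim 1 and is a doubtful yardstick: a plain two-sample calculation at 140 per arm gives Φ(0.12/0.1195 − 1.96) = 17%, not the .91 stated beside it. The value 0.45 comes from the three-arm, 75-father Phase I paragraph.

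Nor is 98 per arm necessarily the Aim 2 sample. It counts fathers with complete treatment and follow-up data, whereas Aim 2 trajectories use measures taken during 18 weeks of treatment. Fathers who miss appointments are phoned or emailed, and partial series can contribute. The effective number may lie nearer 140. For Aim 3, whose outcomes extend to 12 months, 98 is the more apt figure.

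Finally, a reader might infer that a null result will be taken as evidence against the mechanism. No section says so; the risk is one of interpretation.

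**Conclusion.** The adequacy statements for Aims 2 and 3 are unsupported as written, and the Aim 2 sample size is wrong for this design (360/252 against 280/196). Under the stated assumptions, the class-share comparison has about 9–13% power at d = 0.12. At d = 0.45 it is marginal: about 64–71% if only 98 per arm contribute and 79–85% if all 140 do. Class-assignment error or a six-target correction lowers these figures, and the logistic conversion raises them. The class shares, the conversion from d, the error rate and the alpha are assumptions. The failed inference and the wrong total do not depend on them.

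**What to change.** In the AIM 2 paragraph:
- Replace 360/252 with 280/196.
- Delete the inference from 45 cases.
- State that, with error-free classes and a two-sided 5% test of one target, there is 80% power for a class-share difference of about 15–17 percentage points at 140 per arm and 18–20 at 98, and that class-assignment error or correction for six targets widens this.

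In the AIM 3 paragraph, delete the software sentence. State that, under a joint-significance test, power cannot exceed that of the arm-to-class path on the same cases.

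Keep the class-share comparison as the test of 2a and 2b. Replacing it with a mean-change test may look attractive, since at d = 0.45 and 98 per arm a continuous test has 88% power. That gain assumes one normal distribution with no real classes. With true classes at shares 0.50 v 0.674 and within-class SD 1, the mean test at 98 per arm has power 0.415 if the classes lie 2 SD apart (difference 0.347, SE √(3.88/98) = 0.199) and 0.606 at 4 SD (0.695, SE √(9.52/98) = 0.312), against 0.70 for error-free classes. It would also change the stated hypothesis. A continuous growth-factor comparison can be added as supportive only.

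The cost is wording, and a less favourable power statement.

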# Phase I:

Seventy-five fathers of a biological child between 6 months and 11 years who are referred by the Department of Children and Families due to use of domestic violence in the last 12 months, the female co-parent of their youngest child and if different their current female intimate partners of more than 6 months, and their youngest biological child aged 6 months to11 years will participate for a total of up to 240 participants in this Phase 1B randomized controlled trial.

Female intimate partners who are not the co-parent of the youngest child will be contacted if they have been in a relationship with the father for at least 6 months at the time of consent.

# Phase II:

The target sample is 280 father-coparent dyads and their 9 months to 11 year-old children recruited from CPS-involved families referred to the Parent and Family Development Program (PFDP) at Yale or the UCONN Health Center Outpatient Psychiatry Clinic. Participants will be randomized to either F4C (n = 140) or BIP (n = 140) following a baseline assessment. Half of F4C and BIP families will be treated at Yale and half at UConn Health. Yale will serve families in

Greater New Haven region, while UConn Health will serve families in the Greater Hartford region. The two sites are approximately a 45-minute drive apart.

5. **Describe** how access to the population will be gained in the study.

Fathers referred to the Parent and Family Development Program or UCONN Health Center by the CT Department of Children and Families (DCF) or the community due to IPV or child maltreatment risk will be provided information about the study and asked to complete an initial brief screening if they are interested in participation. He will be told that his screening questionnaire (which will include demographic matching information such as age, ethnicity, city of residence, income, employment history, SA history etc.) will be reviewed and he will be contacted to set up further assessment sessions if he is found eligible by the PI based on our study's requirements. This will provide the opportunity for contact with the mother to conduct phone screening with her related to IPV and her willingness for their shared child to participate. Female co-parent and intimate partner contact information will be provided on the referral from DCF or community referral source so that fathers are not providing this information, and this will limit the possibility of coercion.

6. **Participant classification:** Check off all classifications of participants that will be specifically recruited for enrollment in the research project. Will participants who may require additional safeguards or other considerations be enrolled in the study? If so, identify the population of participants requiring special safeguards and provide a justification for their involvement.

🛛 Healthy	□Fetal material, placenta, or dead fetus
Prisoners	□Economically disadvantaged persons
🗆 Employees	□Pregnant women and/or fetuses
□ Females of childbearing pote	ential
	
 
Healthy
 
Prisoners
 
Employees
 
Females of childbearing pote
 

Click or tap here to enter text.

NOTE: Is this research proposal designed to enroll children who are wards of the state as potential participants?  $\square$  Yes  $\square$  No

It is possible that the children of some enrolled fathers will be placed in foster care and under the guardianship of the Department of children and families at the time of referral. These children would only be enrolled if there was planned reunification with the father.

7. **Inclusion/Exclusion Criteria:** What are the criteria used to determine participant inclusion or exclusion?

**Inclusion Criteria**. Men who (1) report an incident of IPV (pushing, slapping, kicking) within the last 12 months prior to screening (based on court/police records, partner or self- report); (2) have at least one biological child aged 9 months to 12 years with whom they have contact in person or by phone/facetime etc. at least monthly; (3) are able to complete assessments in English; and (4) agree to have their female coparents (mother of the youngest child) contacted as collateral informants and for consent for participation of their shared child. If a participant has more than one child in the age range, the youngest will be the target of assessment. Female coparents (the

target child's biological mother who does not need to be in a relationship with the father at the time of the study) will be contacted to consent for participation of herself and their shared child. If the coparent declines participation of the child the father may still participate in the study if he meets eligibility criteria to prevent any possible retaliation against co-parents for not consenting to child participation. No information about contact with co-parents or their responses will be provided to the fathers

**Exclusion Criteria**. Men will be excluded who have: 1) an active full/no contact protective order pertaining to their child since this will preclude participation in the father-child play assessment (many men will have full no-contact orders with their partners, but it is more common for men to still be allowed at least supervised contact with their children even with a full/no contact order with their partner); 2) physiological addiction to a substance that requires detoxification. Fathers will be evaluated using the AUDIT and DAST. If fathers report difficulties with physiological withdrawal from substances (e.g. delirium tremens, shaking, nausea) they will be referred for detox services. They can be re-evaluated following a detox program with documentation from the detox center of successful completion and clean urine screen.; 3) cognitive impairment that will not allow for understanding of the study interventions (a mini mental state score <25); 4) current untreated psychotic disorder; 5) currently suicidal or homicidal based on screening using the BSI; 6) Are currently enrolled or have previously received F4C or BIP; 7)coparent declines to provide collateral information about their child's symptoms.

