# Phase II:

Two hundred eighty fathers, the female *coparent of their youngest child*, and their youngest biological child aged 9 months to 12 years will participate for a total of up to 840 participants in this Phase 2 randomized controlled efficacy trial.

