### SECTION V: RECRUITMENT/CONSENT AND ASSENT PROCEDURES

# 1. Recruitment Procedures:

a. Describe how potential participants will be identified and contacted, and by whom.

Fathers will be provided information about the study at the time of referral by DCF to the Parent & Family Development Program at Yale or the UCONN Health Center. Contact information for co-parents will be provided by DCF or other referral sourc at the time of the referral (which is current practice). Each father will be recruited and given initial screening by a study RA in person or over the phone. If a father expresses interest, an in-person or virtual Zoom appointment will be scheduled to complete informed consent and baseline measures.

Mothers of the fathers' youngest child will be contacted for initial screening and to assess her willingness to allow participation of herself and their shared child in the study. All research staff reaching out to female co-parents or current intimate partners will be trained on phone recruitment strategies used in previous studies by the PI and others to ensure safety of victims of IPV. These include: 1) asking whether she is free to talk now: 2) asking if it is ok to call back again; 3) asking if it is safe to leave messages on her voicemail or via text; and 4) during informed consent, making a plan for the safest way to contact her for follow-up data collection throughout treatment.

Mothers will be interviewed via zoom or in person on different days and encouraged to ensure their safety by choosing a location where they feel safe and away from the father to take the call. Fathers will not be informed of mothers' agreement to participate or the time or location of any contact the study team has with them. They will complete baseline interviews about their relationship history with the father, IPV in the relationship and the father's child maltreatment risk behaviors (hostility, yelling, spanking) toward the child. Mothers and intimate partner baseline interviews will take approximately 1-1 1/2to complete Mothers will be offered \$50 for completion of baseline interviews.

[name] will not be involved in the consent, recruitment, or enrollment of participants.

16

Are you collecting any information about the individuals prior to their signing a consent form? Yes  $\boxtimes$   $\;$  No  $\square$ 

If yes, indicate what information you will be collecting and how it will be gathered (phone screen, paper questionnaire, etc.)

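### The monthly-contact criterion and the target-child rule need not refer to the same child, so a father can enter Phase II with a target child he does not see

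*Combined protocol and SAP*

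**What the plan says.** The contact condition is inclusion criterion 2 in Section IV.7, which asks for "at least one biological child aged 9 months to 12 years with whom they have contact in person or by phone/facetime", no less than once a month. Directly after the list of criteria, the same section chooses the child to be assessed: "If a participant has more than one child in the age range, the youngest will be the target of assessment". The Phase II paragraph of the Research Plan (Section IV.3) says that "their youngest biological child aged 9 months to 12 years will participate". Neither of these last two statements mentions contact.

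The coparent is identified in two ways. Inclusion criterion 4 and the Phase II paragraph point to the mother of the youngest child, and under Section V.1 the mother of a father's "youngest child will be contacted for initial screening and to assess her willingness" to take part. A later sentence of the inclusion criteria instead defines the coparent as the biological mother of the target child.

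Three other provisions bear on the point:

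- Exclusion 1 removes men with "an active full/no contact protective order pertaining to their child since this will preclude participation in the father-child play assessment".
- For children under state guardianship, Section IV.6 says: "These children would only be enrolled if there was planned reunification with the father".
- Exclusion 7 removes the father if the "coparent declines to provide collateral information about their child's symptoms".

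**The concern.** The contact criterion and the target-child rule can select different children. Take a father who sees his 8-year-old every week and has no contact with his 2-year-old. He meets inclusion 2 through the older child, and the younger one becomes the target.

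The Phase II hypotheses on child outcomes are tested on the target child. Hypothesis 1b rests on a recorded play session between the father and that child. Part of 1c rests on the father's account of the child's symptoms, and part of 1a on his behaviour toward the child. Where he does not see the child, the session is unlikely to take place, he has little basis for reporting symptoms, and behaviour directed at that child has little opportunity to occur in either arm. The trial would be collecting weak or missing data on one child while another child, whom it could assess, is left out.

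**Working it through.** The plan states no figure for this point, so the check is mainly one of text.

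**1. Does any provision require contact with the target child?**

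| Provision | What it does | Closes the gap? |
|---|---|---|
| Inclusion 2 (IV.7) | Monthly contact, in person or remote, with at least one child in range | No: any child in range will do |
| Target-child rule (IV.7); Phase II paragraph (IV.3) | Takes the youngest, on age alone | No |
| Exclusion 1 (IV.7) | Removes men under a full no-contact order about their child | No: does not cover absence of contact for other reasons |
| Reunification rule (IV.6) | Covers children under state guardianship | No: that subgroup only |
| Contact frequency (IV.3, Baseline assessments) | Recorded at baseline | No: not an entry test for the target child |
| Residence with target child (IV.3, Stratified Randomization) | Balances the arms | No: does not separate non-resident fathers with contact from those without |
| Participation without the child (V.5) | Lets the father continue if the child does not take part | No: its purpose is to prevent retaliation |

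The gap arises only for fathers with two or more children in range. With one, the contact child and the target child are the same.

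**2. Which outcomes depend on contact?**

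- 1b, coded play (Parent-Child Interaction Tasks): directly dependent.
- 1c, child symptoms: the father's report is weakened. The mother's report does not depend on the father's contact and is required by exclusion 7. Self-report from age 7 does not draw on the father's knowledge, although at baseline it is scheduled in the same appointment as the play session.
- 1a, family violence: behaviour directed at the target child is affected. The partner-violence sources in Table 1 (interview module, abuse inventory from up to three informants, arrest records) do not need father-child contact.

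**3. Illustration of size.** Let p be the share of fathers with an unseen target child. The documents do not give p, so the values below are assumptions. Take a two-group comparison of means, two-sided 5%, 140 per arm (the planned Phase II size, before attrition), normal approximation, set to start at power 0.91:

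- Standardized difference giving power 0.91: d = (1.960 + 1.341) × √(2/140) = 0.395.
- Cases missing: power = Φ(d × √(140(1 − p)/2) − 1.960).
- Cases kept with zero effect: power = Φ(d(1 − p) × √(140/2) − 1.960).

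| p | Per arm with contact | Power, cases missing | Power, kept with zero effect |
|---|---|---|---|
| 0% | 140 | 0.91 | 0.91 |
| 5% | 133 | 0.90 | 0.88 |
| 10% | 126 | 0.88 | 0.84 |
| 20% | 112 | 0.84 | 0.75 |

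The 126 here is 140 × 0.9 and is unrelated to the attrition figure in the plan's power statement. The level 0.91 is borrowed from that statement only as a starting point. The plan attaches it to d = 0.12 in a latent growth model whose inputs are not given, so this table does not test that claim.

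**The case against.** The best defence is a narrower reading. The target-child sentence follows inclusion 2, so a child in the age range could mean a child who meets all of inclusion 2, contact included. The reason given for exclusion 1 points the same way. That reading is reasonable and may be what was intended, but the sentence names only age, and two sites could apply it differently.

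The protocol also records contact. Besides the baseline item, there is a contact and engagement scale in the assessment schedule, and the weekly follow-back calendar logs contact with the target child. Affected families would therefore be identifiable, and residence, the stratification factor nearest to contact, is balanced. None of these is a condition of entry, and no analysis of them is specified.

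The plan accepts some missing play data, since fathers go on to randomization when a session fails. That tolerance protects children who decline; it is no reason to select a child with whom a session is unlikely. Exclusion 7 lowers the number affected further, because the unseen child's mother must agree to give information.

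Three stronger readings are tempting and should be resisted:

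- A reader might infer that the child outcomes as a whole cannot be measured. The mother's report, child self-report and the partner-violence sources contradict that.
- A reader might infer that the treatment effect shrinks in proportion to the share affected. Missing play sessions cost precision. Proportional shrinkage needs cases that are kept and have zero effect, which is not supported for mother-reported symptoms or partner violence. With randomization, systematic bias between the arms is not expected from the selection rule itself.
- A reader might infer that exclusion 1 serves only the play assessment and can be narrowed to the target child. The Initial screen section and the consent-waiver answers in Section V.9 list the order beside severe partner violence as grounds for ineligibility, and Trial Safety makes a new order of this kind a ground for ending the intervention. The documents do not support treating it as a mere practical condition.

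**Conclusion.** The mismatch is real on the text, and no other provision removes it. It concerns fathers with more than one child in range. Its main cost is probable loss of 1b data, with weaker father-reported symptoms and child-directed behaviour; 1c through other informants and the partner-violence part of 1a are largely intact. The size cannot be fixed from the documents. At an assumed 10% share, power would move from 0.91 to about 0.88 if the cases are missing, or 0.84 if they are kept with zero effect. Both figures rest on the simple comparison above and on a share for which the documents offer no anchor. The point is worth correcting because the remedy is specific and cheap.

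The two descriptions of the coparent are a smaller matter. At present they name different women only if the father's youngest child is below the age range and has a different mother. Once the target is tied to contact, they could differ more often, so the wording should be aligned in the same amendment.

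**What to change.** For Phase II, define the target child in Section IV.7 as the youngest biological child in the age range with whom the father has at least monthly contact. Use the same definition in the Phase II paragraph of Section IV.3. Describe the coparent as the target child's biological mother in that paragraph, throughout Section IV.7 (including inclusion criterion 4) and in Section V.1.

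Exclusion 1 does not say which child it concerns. The sponsor should reconcile it with the target-child definition and with the Initial screen, Section V.9 and Trial Safety text. No new rule is proposed here.

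The cost is protocol wording and one item on the screening form. Fathers stay eligible through the child they see. The small downside is that the target will sometimes not be the very youngest child. Remote contact would still satisfy the criterion, so the change does not guarantee in-person contact, although the protocol allows the play session by video conference.
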